### 7.0 TRIAL PROCEDURES

#### 7.1 Trial Procedures

The Trial Flow Chart - Section 6.0 summarizes the trial procedures to be performed at each visit. Individual trial procedures are described in detail below. It may be necessary to perform these procedures at unscheduled time points if deemed clinically necessary by the investigator.

Furthermore, additional evaluations/testing may be deemed necessary by the Sponsor and/or Merck for reasons related to subject safety. In some cases, such evaluation/testing may be potentially sensitive in nature (e.g., HIV, Hepatitis C, etc.), and thus local regulations may require that additional informed consent be obtained from the subject. In these cases, such evaluations/testing will be performed in accordance with those regulations.

#### 7.1.1 Administrative Procedures

#### 7.1.1.1 Informed consent

The Investigator must obtain documented consent from each potential subject prior to participating in a clinical trial.

#### 7.1.1.1.1 General Informed Consent

Consent must be documented by the subject's dated signature or by the subject's legally acceptable representative's dated signature on a consent form along with the dated signature of the person conducting the consent discussion.

The investigator is responsible for patient care and for obtaining consent by the patient. Written informed consent must be obtained prior to entry of any patient. The informed consent will adhere to IRB requirements, applicable laws and regulations and Sponsor requirements.

#### 7.1.1.2 Inclusion/Exclusion Criteria

All inclusion and exclusion criteria will be reviewed by the investigator or qualified designee to ensure that the subject qualifies for the trial.

## 7.1.1.3 Medical History

A medical history will be obtained by the investigator or qualified designee. Medical history will include all active conditions, and any condition diagnosed within the prior 10 years that are considered to be clinically significant by the Investigator. Details regarding the disease for which the subject has enrolled in this study will be recorded separately and not listed as medical history.

### 7.1.1.4 Prior and Concomitant Medications Review

#### 7.1.1.4.1 Prior Medications

The investigator or qualified designee will review prior medication use, including any protocol-specified washout requirement, and record prior medication taken by the subject within 28 days before starting the trial. Treatment for the disease for which the subject has enrolled in this study will be recorded separately and not listed as a prior medication.

#### 7.1.1.4.2 Concomitant Medications

The investigator or qualified designee will record medication, if any, taken by the subject during the trial. All medications related to reportable SAEs and ECIs should be recorded as defined in Section 7.2.

#### 7.1.1.5 Disease Details and Treatments

#### 7.1.1.5.1 Disease Details

The investigator or qualified designee will obtain prior and current details regarding disease status.

#### 7.1.1.5.2 Prior Treatment Details

The investigator or qualified designee will review all prior cancer treatments including systemic treatments, radiation and surgeries.

### 7.1.2 Assignment of Screening Number

Once a patient is enrolled in the study, he/she will be assigned a simple 3 digit number, with the first patient assigned to 001 and so on. A separate spreadsheet with password protection will be maintained that contains the patient study number along with personally identifiable information. Password protection will be maintained in order to keep patient information strictly confidential. Upon signing the informed consent form, the patient will be assigned a subject number by the investigator or his/her designee. Once assigned to a patient, a subject number will not be reused. If the patient fails to be started on treatment for any reason, the reason will be entered on the Eligibility Tab in OnCore, and his/her demographic information will be entered on the Demography Tab in OnCore. All laboratory, radiologic, and pathologic data collected on trial participants will be assigned the unique treatment number and stored in the OnCore system database.

#### 7.1.3 Assignment of Randomization Number

Patients who successfully complete the screening exams for initial registration will be randomized into one of two study arms. Randomization will be accomplished using the Moffitt Cancer Center web-based Subject Registration and Randomization System (SRAR). The SRAR program is accessed using an individual secure identification key that authenticates the user into the Moffitt network

The study Biostatistician will generate a Flow Chart for Randomization. This Flow Chart will be held in confidence by the Biostatistician and the Clinical Trials Coordinator. The individual randomization assignment will be released by the Clinical Trials Coordinator only after the patient signs the informed consent document and successfully completes the screening process.

**Treatment of patients on Arm A:** Those patients randomized to Arm A will receive pembrolizumab alone.

**Treatment of patients on Arm B**: Those patients randomized to Arm B will receive pembrolizumab plus vorinostat.

## 7.1.3.1 Trial compliance (medication/diet/activity/other)

The Principal Investigator and the Clinical Research Coordinator assigned to the case will be primarily responsible for maintaining all study related documents including the clinical research forms. Oncore is the password protected, web-based electronic secure, database of record for all CRF entries and will be verified with source documentation. The review of medical records within the EMR will be done in a manner to assure that patient confidentiality is maintained. Vorinostat compliance review will take place via a medication diary review as indicated in the study calendar.

#### 7.1.4 Clinical Procedures/Assessments

## 7.1.4.1 Adverse event (AE) monitoring

AEs will be collected from time of C1D1. The investigator or qualified designee will assess each subject to evaluate for potential new or worsening AEs as specified in the Trial Flow Chart and more frequently if clinically indicated. Adverse experiences will be graded and recorded throughout the study and during the follow-up period according to NCI CTCAE Version 4.0 (see Section 11.2). Toxicities will be characterized in terms regarding seriousness, causality, toxicity grading, and action taken with regard to trial treatment.

For subjects receiving treatment with pembrolizumab all AEs of unknown etiology associated with pembrolizumab exposure should be evaluated to determine if it is possibly an event of clinical interest (ECI) of a potentially immunologic etiology (termed immune-related adverse events, or irAEs); see the separate ECI guidance document in Appendix 4 regarding the identification, evaluation and management of potential irAEs.

Please refer to section 7.2 for detailed information regarding the assessment and recording of AEs.

## 7.1.4.2 Full physical exam

The investigator or qualified designee will perform a complete physical exam during the screening period. Clinically significant abnormal findings should be recorded as medical history. A full physical exam should be performed during screening,

## 7.1.4.3 Directed physical exam

For cycles that do not require a full physical exam per the Trial Flow Chart, the investigator or qualified designee will perform a directed physical exam as clinically indicated prior to trial treatment administration.

## 7.1.4.4 Vital signs

The investigator or qualified designee will take vital signs at screening, prior to the administration of each dose of trial treatment and at treatment discontinuation as specified in the Trial Flow Chart (Section 6.0). Vital signs should include temperature, pulse, respiratory rate, weight and blood pressure. Height will be measured at screening only.

## 7.1.4.5 Eastern Cooperative Oncology Group (ECOG) Performance Scale

The investigator or qualified designee will assess ECOG status (see Section 11.1) at screening, prior to the administration of each dose of trial treatment and discontinuation of trial treatment as specified in the Trial Flow Chart.

## 7.1.4.6 Tumor imaging and assessment of disease

Patients will undergo a CT Thorax and Abdomen at baseline, then every 2 cycles. After 1 year of follow-up, the interval of CT will be extended to once every 12 weeks. Radiographic assessments will be based on Response Evaluation Criteria in Solid Tumors v1.1 (RECIST v1.1). Subjects with progressive disease by RECIST v1.1 but without rapid clinical deterioration may continue to be treated at the discretion of the investigator.

Baseline Brain MRI or Brain CT will be required.

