#### 5.2.1.2 Dose Modification

Adverse events (both non-serious and serious) associated with pembrolizumab exposure may represent an immunologic etiology. These adverse events may occur shortly after the first dose or several months after the last dose of treatment. Pembrolizumab must be withheld for drug-related toxicities and severe or life-threatening AEs as per **Table 7** below. See Section 5.6.1 and Events of Clinical Interest Guidance Document for supportive care guidelines, including use of corticosteroids.

Table 7. Dose Modification Guidelines for Drug-Related Adverse Events

Toxicity	Hold Treatment For Grade	Timing for Restarting Treatment	Discontinue Subject
Diarrhea/Colitis	2-3	Toxicity resolves to Grade 0-1.	Toxicity does not resolve within 12 weeks of last dose or inability to reduce corticosteroid to 10 mg or less of prednisone or equivalent per day within 12 weeks.
	4	Permanently discontinue	Permanently discontinue
AST, ALT, or Increased Bilirubin	2	Toxicity resolves to Grade 0-1	Toxicity does not resolve within 12 weeks of last dose.
	3-4	Permanently discontinue (see exception below) 	Permanently discontinue
Type 1 diabetes mellitus (if new onset) or Hyperglycemia	T1DM or 3-4	Hold pembrolizumab for new onset Type 1 diabetes mellitus or Grade 3- 4 hyperglycemia associated with evidence of beta cell failure.	Resume pembrolizumab when patients are clinically and metabolically stable.
Hypophysitis	2-3	Toxicity resolves to Grade 0-1	Toxicity does not resolve within 12 weeks of last dose or inability to reduce corticosteroid to 10 mg or less of prednisone or equivalent per day within 12 weeks.
	4	Permanently discontinue	Permanently discontinue
Hyperthyroidis m	3	Toxicity resolves to Grade 0-1	Toxicity does not resolve within 12 weeks of last dose or inability to reduce corticosteroid to 10 mg or less of prednisone or equivalent per day within 12 weeks.
	4	Permanently discontinue	Permanently discontinue
Hypothyroidism	2-4	Therapy with pembrolizumab can be continued while treatment for the thyroid disorder is instituted	Therapy with pembrolizumab can be continued while treatment for the thyroid disorder is instituted.
Infusion Reaction	3-4	Permanently discontinue	Permanently discontinue
Pneumonitis	2	Toxicity resolves to Grade 0-1	Toxicity does not resolve within 12 weeks of last dose or inability to reduce corticosteroid to 10 mg or less of prednisone or equivalent per day within 12 weeks.

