## 5.2.2 Timing of Dose Administration

Trial treatment should be administered on Day 1 of each cycle after all procedures/assessments have been completed as detailed on the Trial Flow Chart (Section 6.0). There is a ±7 day treatment window for Day 1 of each cycle.

All trial treatments will be administered on an outpatient basis.

Pembrolizumab 200 mg will be administered as a 30 minute IV infusion every 3 weeks. Sites should make every effort to target infusion timing to be as close to 30 minutes as possible. However, given the variability of infusion pumps from site to site, a window of -5 minutes and +10 minutes is permitted (i.e., infusion time is 30 minutes: -5 min/+10 min).

The Pharmacy Manual contains specific instructions for the preparation of the pembrolizumab infusion fluid and administration of infusion solution.

Vorinostat should be taken with food, at regular intervals regardless of pembrolizumab infusion time. On days the pt receives pembrolizumab, the vorinostat should be taken prior to pembrolizumab infusion.

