## **6.0 TRIAL FLOW CHART**

## 6.1 Study Flow Chart\*

Trial Period:		Treatment Cycles								End of Treatment	Post-Treatment		
	Study					To be		ated be	eyond		Safety		Survival
Treatment Cycle/Title:	Screening (Visit 1)	1	2	3	4	5	6	7	8	Discon	Follow- up	Follow Up Visits	Follow- Up
Scheduling Window (Days):	-27 to c1d1 e		± 7	± 7	± 7	± 7	± 7	± 7	± 7	At time of Discon	30 days post last dose of study drug	Every 8 weeks post discon	Every 12 weeks
Screening Consent	Χ												
Informed Consent	Х												
Inclusion/Exclusion Criteria	Х												
Demographics and Medical History	Х												
Prior and Concomitant Medication Review	Х	Х	Х	х	Х	Х	х	Х	Х				
Vorinostat compliance review/Pill Diary		Х	Х	х	Х	Х	Х	Х	Х	Х			
Trial Treatment Administration		Х	Х	Х	Х	Х	Х	Х	Х				
Post-study anticancer therapy status										×	Х		Х
Survival Status		Х	Х	Х	Х	Х	Х	Х	Х	Х			Х
Review Adverse Events	Χ †	Х	Х	Х	Х	Х	Х	Х	Х	Х	Х		
Full Physical Examination	Х												
Directed Physical Examination		Х	Х	Х	Х	Х	Х	Х	Х	Х	Х		
Vital Signs and Weight	Х	Х	Х	Х	Х	Х	Х	Х	Х	Х	Х		
ECOG Performance Status	Х	Х	Х	Х	Х	Х	Х	Х	Х		Х		
Pregnancy Test – Urine or Serum b-HCG	Х	Х	Х	Х	Х	Х	Х	Х	Х		Х		

Trial Period:					Cycle	es				End of Treatment	Post-Treatment		
	Study					To be		ated be	eyond		Safety		Survival
Treatment Cycle/Title:	Screening (Visit 1)	1	2	3	4	5	6	7	8	Discon	Follow- up	Follow Up Visits	Follow- Up
Scheduling Window (Days):	-27 to c1d1 e		± 7	±7	± 7	±7	± 7	± 7	± 7	At time of Discon	30 days post last dose of study drug	Every 8 weeks post discon	Every 12 weeks
PT/INR and aPTT	Х	X (C1D15 -C1D21											
CBC with Differential	Х	Х	Х	Х	Х	Х	Х	Х	Х		Х		
Comprehensive Serum Chemistry Panel	Х	Х	Х	х	Х	Х	Х	Х	Х	Х	Х		
Magnesium	Х	Х	Х	Х	Х	Х	Х	Х	Х	Х	Х		
Urinalysis	Х												
T3, FT4 and TSH	Х	Х	Х	Х	Х	Х	Х	Х	Х	Х	Х		
Echocardiogram g	Х												
EKG	Х												
Tumor Imaging (CT Thorax/Abdomen)	Х			Х		Х		Х		Х		X d	
Brain MRI or Brain CT	Х												
Archival or Newly Obtained Tissue Collection a,b	Х	X (C1D15 -C1D21											
Correlative Studies Blood Collection c	X c	X c		Х		Х		Х		Х		Х	

Trial Period:		Treatment Cycles						End of Treatment	Po	st-Treatme	nt		
	Study					To be		ated be	yond		Safety		Survival
Treatment Cycle/Title:	Screening (Visit 1)		2	3	4	5	6	7	8	Discon		Follow Up Visits	Follow- Up

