Scheduling Window (Days):	-27 to c1d1 e		± 7	± 7	± 7	± 7	± 7	± 7	± 7	At time of Discon	30 days post last dose of study drug	Every 8 weeks post discon	Every 12 weeks

\*All clinic visits and tests (including labs, imaging studies and biopsies) will have a plus or minus 7 day window for completion.

<sup>a All patients in the study are required to have a pre-treatment biopsy, where feasible, or archival tissue from after the most recent line of therapy, which will be tested for PD-L1 and nanostring analyses.

<sup>b C1D15-21 biopsies will be done on patients in the phase I dose escalation, phase Ib and phase II parts of the study, where feasible. PD-L1 and Nanostring studies will be completed on all of these biopsy specimens.

<sup>c Timepoints for the first two correlative study blood collection include first during Screening or on C1D1, and second on C1D15. The remainder of the blood collections will occur with the reimaging scans. Histone acetylation studies will be run on serial PBMC draws in all patients (includes phase I dose escalation, phase Ib expansion and phase II). The blood will be collected in five 10 mL green top (sodium heparin) tubes for a total of about 50mL of whole blood.

<sup>d Subjects who discontinue trial treatment for a reason other than disease progression will move into the Follow-Up Phase and should be assessed every 8 weeks (56 ± 7 days) by radiologic imaging to monitor disease status. After 1 year, the imaging time point will occur every 12 weeks (± 7 days).

<sup>e The main study screening window will occur within 28 days prior to the first study treatment. Note additionally that screening laboratory blood and urine studies must be obtained within 10 days of C1D1, with the exception of pregnancy testing in applicable patients, which must be obtained within 72 hours of first treatment.

f Only serious adverse events will be collected during the screening window.

<sup>9 Echocardiogram will be performed at screening for baseline, and may be repeated if clinically indicated per the treating investigator. Echocardiogram should be performed within 30 days of treatment initiation.

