#### 7.1.7.2 Follow-up visits

Subjects who discontinue trial treatment for a reason other than disease progression will move into the Follow-Up Phase and should be assessed every 8 weeks (56  $\pm$  7 days) by radiologic imaging to monitor disease status. After 1 year, the imaging time point will occur

every 12 weeks (± 7 days). Every effort should be made to collect information regarding disease status until the start of new anti-neoplastic therapy, disease progression, death, end of the study or if the subject begins retreatment with pembrolizumab as detailed in Section 7.1.7.3. Information regarding post-study anti-neoplastic treatment will be collected if new treatment is initiated.

Subjects who are eligible to receive retreatment with pembrolizumab according to the criteria in Section 7.1.7.3 will move from the follow-up phase to the Second Course Phase when they experience disease progression.

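### First-year on-treatment scans follow cycle number, not calendar weeks, so PFS and duration of response could lean towards Arm B if it has more long dose holds

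*Combined protocol and SAP*

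**What the plan says.** Section 7.1.4.6 sets the routine schedule: "Patients will undergo a CT Thorax and Abdomen at baseline, then every 2 cycles". The flow chart (section 6.1) marks CT under screening, cycles 3, 5 and 7, and discontinuation, with no week numbers. Its general footnote says that visits and tests, imaging included, "will have a plus or minus 7 day window for completion", but does not say from which date the window runs.

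Pembrolizumab dosing sets the cycle length. Section 5.2.2: "Pembrolizumab 200 mg will be administered as a 30 minute IV infusion every 3 weeks", so two cycles are nominally 6 weeks. The same section adds: "There is a ±7 day treatment window for Day 1 of each cycle". Section 5.2.1.2 allows non-toxicity interruptions of up to 3 weeks, or longer after discussion with the sponsor. For most toxicities that require a hold, Table 7 takes the patient off only when "Toxicity does not resolve within 12 weeks of last dose" or steroids cannot be reduced in that time.

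Other scans are timed by the calendar:
- Section 7.1.4.6: "After 1 year of follow-up, the interval of CT will be extended to once every 12 weeks".
- Section 7.1.7.2: patients who stop treatment without progression "should be assessed every 8 weeks", then every 12 weeks after 1 year.
- Section 4.2.3.1: a response is confirmed 4-6 weeks later.
- Section 4.2.11: patients treated beyond progression have a follow-up scan within about 6 weeks.

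None of these puts routine first-year on-treatment scans back on calendar time after a hold.

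Section 4.2.6 derives PFS from scan dates. Section 3.1 names PFS beside response rate in the phase II primary hypothesis. Section 8.2.5 calls response rate the primary endpoint.

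**The concern.** Progression is recorded at the first scan after it occurs. If scans move with the doses, a held patient is scanned later and progression is dated later, although the disease has not behaved differently. With equal delays in both arms, the comparison is largely protected. With more delay in one arm, that arm's Kaplan-Meier PFS curve is shifted to the right. Duration of response is lengthened in the same way when the hold comes after the response.

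Arm B adds vorinostat at a dose chosen for a 30% DLT rate (section 8.2.3). A 16-patient vorinostat trial cited in section 4.2.1, on other dosing schedules, reported 50% grade 3/4 thrombocytopenia. More cycle delays in Arm B are therefore plausible. The trial is open label, so blinding does not help keep delays similar.

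**Working it through.** **1. The plan's own figures.** No stated figure depends on scan timing. The power in section 8.4 uses responses only. Exact binomial calculation of the rule in section 8.2.6 (5/23, then 13/39) gives a pass probability of 0.9009 at a 45% response rate and 0.0845 at 25%. When both arms pass, Arm B wins on the posterior rule with probability 0.0337. Power = 0.9009 × (1 − 0.0845) + 0.0337 = 0.858, against 87% stated. With 25% in both arms the result is 0.0775, against 8.06% stated. PFS enters neither figure.

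**2. How far a scan can move.** Nominal gap: 2 × 3 = 6 weeks. The 12-week limit runs from the last dose, so the longest slip past the due dose is 12 − 3 = 9 weeks. One such hold makes the gap 6 + 9 = 15 weeks. The overall median PFS quoted in section 4.2.1 is 3.7 months: 3.7 × 365.25 / 12 / 7 = 16.1 weeks. With exponential PFS at that median, 1 − 2^(−52/16.1) = 89% of progressions or deaths fall in year 1, the exposed period.

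**3. Size under no true difference.** Both arms have exponential PFS with median 16.1 weeks and progression dated at the next scan. Scans fall every two 3-week cycles, and each cycle is held with an assumed probability. The documents give no hold rates. The error yardstick is a one-sided 10% log-rank test with 39 per arm and 1,500 runs (standard error about 0.008). It is supplied for this check and is not in the plan. The no-hold row has no holds in either arm; in the other rows Arm A is held in 5% of cycles.

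| Arm B cycles held | Hold | Mean detected progression, B − A (weeks) | False 'B better' |
|---|---|---|---|
| none | – | 0.04 | 9.4% |
| 10% | 3 wk | 0.30 | 9.7% |
| 15% | 3 wk | 0.46 | 10.7% |
| 20% | 3 wk | 0.55 | 12.5% |
| 30% | 3 wk | 0.96 | 12.8% |
| 15% | 6 wk | 0.95 | 14.3% |
| 20% | 6 wk | 1.41 | 16.0% |
| 15% | 9 wk | 1.63 | 16.2% |
| 20% | 9 wk | 2.25 | 20.2% |

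The apparent hazard ratio is about 0.94 at 20% with 6-week holds and 0.89 at 20% with 9-week holds. The same calculation gave 1.02 with no holds, so read these to within about 0.02. The median is a poor gauge because it can only land on scan dates: 18 v 18 weeks with no holds, 18 v 21 for 3-week holds at 15-30%, 18 v 24 for 6-week holds at 20%, and 21 v 21 for 9-week holds.

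A milder model allows at most one hold per patient, in Arm B only (2,000 trials per setting, standard error about 0.007). False 'B better' is 11.2% with no holds. It is 9.1% and 9.2% with 3-week holds in 30% and 50% of patients, 10.4% with 6-week holds in 30%, and 13.8% with 6-week holds in 50%. Only the last exceeds the baseline.

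**4. With calendar scans.** Fixing scans every 6 weeks gives mean detected progression of 26.3 v 26.4 weeks, median 18 weeks in both arms, and 9.6% false 'B better'.

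**5. Disease control.** The share progression-free at the first scan is 2^(−6/16.1) = 77% at week 6 and 2^(−12/16.1) = 60% at week 12. A later first scan therefore lowers recorded disease control.

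**The case against.** The strongest reply is that the imbalance is assumed. Table 7 is written around pembrolizumab, and pembrolizumab sets the cycle clock. The plan does not say whether interrupting vorinostat alone delays a cycle; if it does not, the difference between arms shrinks. Section 4.2.1 also says that the two drugs' toxicities overlap little. This stands, and it is why the point is conditional.

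The larger simulated effects also need heavy hold rates. At 20% per cycle, 1 − 0.8^6 = 74% of Arm B would be held at least once in six cycles. This stands too: short or infrequent holds do little.

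The plan has partial safeguards: a scan at discontinuation, unscheduled procedures where clinically necessary (section 7.1), and the calendar-timed scans listed above. They limit the delay but do not restore the routine schedule during a hold.

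A reader might infer that holds raise Arm B's chance of being declared the winner, or its disease control rate. The documents do not support either. The winner rule in sections 8.2.4 and 8.2.6 counts responses, and no between-arm PFS test or alpha is specified, so no stated error rate changes. Delayed scans give fewer early chances to record a response and more time to progress before stable disease is recorded. Both work against Arm B.

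**Conclusion.** The gap in the text is real, and no other section closes it: routine first-year on-treatment scans move with the cycles while PFS is dated by scan. The exposure is limited to the Kaplan-Meier PFS and duration-of-response estimates, and the bias favours Arm B only if Arm B has more cycle delays. It is negligible or small for 3-week holds. It becomes material only if long holds are common in Arm B: about 1.4 to 2.3 weeks later mean detected progression at 20% of cycles held for 6 to 9 weeks.

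These sizes rest on assumed hold rates, exponential PFS and a 16.1-week median taken from an overall pembrolizumab population. A longer median in the PD-L1-positive phase II patients would make a given delay matter less. Treatment discontinuation and the wider scan interval after year 1 were not modelled.

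It would go too far to say that Arm B's progression dates will be pushed back, or that doses may slip by 12 weeks; the longest slip past the due dose is about 9. This is a cheap improvement, not a threat to the trial's decision rule.

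**What to change.** In section 7.1.4.6 and the flow chart, schedule CT every 6 weeks (±7 days) by calendar date from Cycle 1 Day 1, in both arms, regardless of dose delays. Replace the cycle-column marks with week numbers and keep the 12-week interval after 1 year. In section 7.1.7.2 and the matching flow chart footnote, put scans after stopping treatment but before progression on the same calendar, in place of the 8-week interval. Otherwise, arms that stop treatment at different rates are scanned at different intervals.

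Scan timing would then no longer depend on whether holding vorinostat alone delays a cycle. No dosing rule changes, and the planned on-treatment frequency stays the same. The cost is protocol wording, some scans on non-dosing visits, and slightly more frequent scans for patients who stop early. If patients have already been scanned on slipped dates, an interval-censored PFS sensitivity analysis would help, though it can only partly repair the timing.
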